2. By strengthening the lateral pterygoid muscle and learning a properly executed lower jaw sideways movement, the cracking phenomenon during jaw opening or jaw closing movements in patients with an anterior disc displacement with reduction is reduced.

Study design

Prospective, randomized study with control group, stratified by gender.

The type of therapy is assigned randomly.

The study is unblinded for the doctor and patient.

It is not possible to blind the practitioner because he is familiar with the forms of treatment. Since the practitioner and examiner are one and the same person in the practice, blinding is not possible here either.

It is also not possible to blind the patient, as they are able to research the form of therapy. During the last examination, the participants of the study are asked whether they have researched the respective form of treatment.

Target criteria

Primary outcome variable

The primary outcome variable is defined as the change of orofacial pain in the head and joint area after initiating the therapy measured by numeric rating scale (NRS; 0-10, 0: no pain, 10: worst imaginable pain) at the time of the follow-up appointments.

Secondary outcome variables

The following parameters are recorded as secondary target variables:

- Change in number of clicking noises in the TMJ during jaw opening or jaw closing movements
- Change in force degrees for lateral movement of the mandible according to Janda (modified scale from 4- to 5)

- Change in interincisal distance during maximum unassisted opening (in mm)

Sample size estimation

Determine the required sample size based on the numerical pain scale 0-10 for the primary target variable. Norms are pain scores of 3-5 (myofascial pain) in patients with craniomandibular dysfunction (CMD). To determine a mean difference of 2 level (standard deviation of 2 between the two treatment groups, they must each comprise 24 patients.

Test method: Wilcoxon-Mann-Whitney test with a two-sided α = 0.05, a power = 0.90 assuming the family of logistic distributions (G * Power, version 3.1.) The net sample consists of 48 persons. Assuming a drop out 6 patients per group, a total sample of 60 persons must be calculated.

Methods of data collection

The data is collected electronically and saved in the patient file. The required values for each patient were taken from the computer system of Dr. med. dent. [name]'s dental practice.

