In addition, the study groups are differentiated according to the categorical factor of gender.

Statistical analysis

The evaluation of the target variables is carried out using descriptive and inductive statistics.

In the descriptive statistical representation, the usual characteristic values such as frequency, mean values, standard deviation and range of values (minima, maxima) are used.

Possible differences in the study groups are analyzed using parametric (double t-test) and non-parametric (Mann-Whitney U-test) methods. The Chi²- test is used to analyze possible relationships between the nominally scaled values (e.g. gender). The interpretation is based on a 95% confidence interval. The hypothesis testing procedure is based on an error probability of 5% [p = 0.05], which is often used in studies.

The evaluation of the blinded data is carried out by [name].

Data management

Data collection

The data for each patient are taken from the electronic patient file of Dr. med. dent. [name] in Steina. This includes the questionnaire consisting of the baseline exmaination, x-rays, functional status, as well as the primary (pain when opening or closing the mouth) and secondary (occurrence of the cracking phenomenon when opening or closing the mouth, Janda degrees of strength in laterostrusion movement, interincisal opening distance) target variables.

The forms are filled out, dated and signed by the test subjects or persons who are authorized to document them (dental practice employees).

Data processing

The data entry in the electronic patient file is carried out by the examiner Dr.med.dent. [name] or his employees. All questionnaires and findings sheets that have been filled out by hand are scanned and also saved in the electronic file of each volunteer.

The use of the data takes place in accordance with legal regulations and requires a voluntarily submitted and signed declaration of consent by the test persons before participating in the clinical study.

The collected data may be passed on to [name] and the study director in pseudo-anonymized form for the purpose of scientific evaluation.

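### The pain comparison is planned without adjustment for baseline NRS or the gender stratum: valid, but in several plausible cases less efficient than an ANCOVA on data already collected

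*Combined protocol and SAP*

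**What the plan says.** The SAP's Statistical analysis section opens with "The evaluation of the target variables is carried out using descriptive and inductive statistics" and gives the method for group comparisons as "Possible differences in the study groups are analyzed using parametric (double t-test) and non-parametric (Mann-Whitney U-test) methods". It adds "The interpretation is based on a 95% confidence interval". No section names a covariate, a regression model or a stratified test.

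Under Primary outcome variable, "The primary outcome variable is defined as the change of orofacial pain in the head and joint area after initiating the therapy". The Abstract has NRS measured at baseline and at 2, 4 and 6 months, so the baseline value is available.

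The Randomization section stratifies by gender and justifies this by gender's predictive strength for temporomandibular dysfunction. In the SAP, gender appears twice. The groups are to be distinguished by it (Number of cases), with no test attached, and it is the example for the Chi² test of nominal variables. Neither adjusts the pain comparison.

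Under Sample size estimation: "To determine a mean difference of 2 level (standard deviation of 2 between the two treatment groups, they must each comprise 24 patients" and "Test method: Wilcoxon-Mann-Whitney test with a two-sided α = 0.05, a power = 0.90 assuming the family of logistic distributions". Then: "Assuming a drop out 6 patients per group, a total sample of 60 persons must be calculated".

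**The concern.** A change score fixes the weight of baseline pain at 1, and a follow-up score fixes it at 0. ANCOVA estimates that weight, so its residual SD cannot exceed that of either. When r is low, subtracting baseline adds noise, and a change-score test can have less power than planned. Leaving out a prognostic stratum that was balanced by design also makes the unadjusted tests somewhat conservative.

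At stake are the power of the primary comparison and the width of the 95% interval on which interpretation rests. The Mann-Whitney test used for the sample size does not by itself give an interval for the mean difference.

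**Working it through.** **Inputs from Sample size estimation:** difference 2, SD 2, two-sided α 0.05, power 0.90, 24 per arm. **Not in the documents, so assumed:** r, the baseline SD and the share of outcome variance due to gender.

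**The plan's own figure.** The normal approximation is 2 × (1.960 + 1.282)² × (2/2)² = 21.0, so 22 per arm. The noncentral t-test gives 23. Mann-Whitney by asymptotic relative efficiency gives 24 for a normal parent (factor 3/π, power 0.912) and 21 for the logistic parent the protocol names (factor π²/9 = 1.097). So 24 is reproduced for a normal parent and is generous for a logistic one. Dropout: 6/30 = 20%, and 48/0.80 = 60.

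**Method.** Power is by noncentral t at difference 2 and 24 per arm. Mann-Whitney uses an effective n of 24 × 1.097. ANCOVA has 48 − 4 = 44 degrees of freedom, against 46 for the t-test. With SD exactly 2 for the tested variable, the t-test has 0.924 and Mann-Whitney 0.945. ANCOVA at r = 0 has 0.923.

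**A. SD 2 is the SD of scores, equal at both times; change is tested.** SD of change = 2√(2(1−r)); ANCOVA residual SD = 2√(1−r²). At r = 0.3 these are 2.37 and 1.91.

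| r | t-test | Mann-Whitney (logistic) | ANCOVA |
|---|---|---|---|
| 0.2 | 0.77 | 0.80 | 0.93 |
| 0.3 | 0.82 | 0.85 | 0.94 |
| 0.4 | 0.87 | 0.90 | 0.96 |
| 0.5 | 0.92 | 0.945 | 0.97 |
| 0.6 | 0.97 | 0.98 | 0.99 |

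Power reaches 0.90 at r = 0.45 (t-test) and 0.40 (Mann-Whitney, logistic; 0.48 if normal). With no dropout (30 per arm) these become 0.31 and 0.24 (0.34 if normal). The 95% CI half-width is t × SD × √(2/24). At r = 0.3 it is 1.38 NRS points unadjusted and 1.11 with ANCOVA; at r = 0.5 it is 1.16 and 1.01.

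**B. SD 2 is the SD of change.** The score SD is then 2/√(2(1−r)), and the ANCOVA residual SD is 2√((1+r)/2). The t-test has 0.92 and Mann-Whitney 0.945 throughout. ANCOVA has 0.987, 0.974, 0.957 and 0.946 at r = 0.3, 0.5, 0.7 and 0.8. At r = 0.8 nothing is gained over Mann-Whitney.

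**C. Follow-up scores are tested, SD 2.** The planned tests again have 0.92 and 0.945. ANCOVA has 0.944, 0.974 and 0.997 at r = 0.3, 0.5 and 0.7, so there is no gain over Mann-Whitney at r = 0.3.

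**D. The NRS≥3 entry rule narrows the baseline SD, assumed 1.25; follow-up SD 2; change is tested.** Variance of change = 1.25² + 4 − 4 × 1.25 × r.

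| r | t-test | Mann-Whitney (logistic) | ANCOVA |
|---|---|---|---|
| 0.2 | 0.888 | 0.915 | 0.933 |
| 0.3 | 0.920 | 0.942 | 0.944 |
| 0.4 | 0.949 | 0.965 | 0.959 |
| 0.5 | 0.972 | 0.982 | 0.974 |

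Mann-Whitney matches ANCOVA at r = 0.32 and exceeds it by at most 0.008 above that.

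**Gender.** If gender explained an assumed 2, 5 or 10% of outcome variance, adjusting for it alone would raise t-test power from 0.924 to 0.928, 0.935 or 0.947 (SD 2√(1−R²), 45 degrees of freedom).

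**Validity.** Simulation used 20,000 runs, 24 per arm, r = 0.5 and 75% women, all assumed. With a gender effect of 0, 0.5 or 1.0 SD, the type I error of the change t-test was 0.048, 0.046 and 0.033. For Mann-Whitney on follow-up scores it was 0.049, 0.045 and 0.032. ANCOVA stayed at 0.049 to 0.051. The planned tests are at or below nominal level.

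**The case against.** The strongest reply is that the loss may be slight.

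- The sample size paragraph says it is based on the primary variable, which is a change. On that reading SD 2 is the SD of change (case B), and the planned tests exceed 0.90.
- Case A assumes equal SDs, while the entry rule truncates only the baseline. Case D then leaves little or no gain over Mann-Whitney.
- The Mann-Whitney figures assume that the tested variable itself is logistic.
- Gender is called a predictor of the disorder, not of NRS pain among patients who already have it.
- A linear model on a bounded integer score brings assumptions that the rank test avoids.

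Much of this stands as a limit on size. Case B is at least as natural a reading as case A, although the sentence just before the SD speaks of pain scores, so the text does not settle it. The gender gain cannot be quantified from the documents.

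Floor effects also matter. In simulations with integer scores clipped at 0 (assumed baseline mean 4 to 5, follow-up means 3 vs 1 or 2.5 vs 0.5 before clipping, low r), the realised difference shrank to 1.5 to 1.7 and ANCOVA power to about 0.88 to 0.91. ANCOVA still beat the change-score tests there. The objection therefore does not restore the unadjusted tests as the better choice.

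**Conclusion.** The point holds as a recommended improvement. The planned tests are valid but make no use of baseline NRS as a covariate or of the gender stratum in comparing pain.

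The loss runs from nil to substantial: about 0.09 to 0.13 in power at r = 0.3 in case A, less in case B, and negligible or slightly reversed against Mann-Whitney in case D from about r = 0.3. Confidence is high on the omission and on the validity of the tests. The size is conditional on r, the baseline SD and the meaning of SD 2.

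At a true difference of 2 and SD 2 under either reading, ANCOVA has power of about 0.92 or more. The formula floor is 0.923; simulation with chance baseline imbalance gives about 0.918 at r = 0.

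**What to change.** - **SAP, Statistical analysis.** Make the primary analysis an ANCOVA of NRS on treatment, baseline NRS and gender, at the visit the sponsor designates as primary (none is designated now). Report the adjusted difference with 95% CI and p-value. Modelling the change instead gives the identical treatment difference, so the outcome definition can stand.
- **Sensitivity analysis.** Pre-specify the Mann-Whitney test, or its gender-stratified (van Elteren) form, because the score is bounded.
- **Sample size estimation.** State whether SD 2 refers to scores or to change. State also that 24 per arm was derived for the Wilcoxon-Mann-Whitney test and remains sufficient for the ANCOVA (about 0.92 at difference 2 and SD 2), so that the sample size and the primary test agree.

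The cost is SAP wording, two sentences in the sample size section, one regression model, two degrees of freedom (44 instead of 46) and linear-model assumptions, which the rank test checks. The sample size, visits and data collection do not change.
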